## APPENDIX E. CLINICAL LABORATORY AND VITAL SIGN SAFETY ENDPOINTS

This appendix lists endpoints and cut-off points for vital signs, physical findings, and other observations related to safety. Summary tables by visit, and by-subject listings in select cases, will be provided for all outcomes, observed and change from baseline, in this section. All listings will be sorted by treatment group, subject, parameter, and time period as appropriate.

If the central laboratory uses assays that have lower limits of detection (LLD), all laboratory results below the LLD will be imputed with the LLD. Results reported as greater than a value (i.e., “> value”) will be imputed as  $1.5 \times$  that value.

### E.1. Clinical Laboratory Evaluation

#### E.1.1 Liver Function Abnormality

A summary of liver function abnormalities by analysis period will be provided by treatment group.

Any subject with at least 1 of the following liver function abnormalities will be summarized:

- Alanine aminotransferase (ALT)  $>2 \times$  and  $\leq 3 \times$  upper limit of normal (ULN); ALT  $>3 \times$  and  $\leq 5 \times$  ULN; ALT  $>5 \times$  and  $\leq 10 \times$  ULN; ALT  $>10 \times$  ULN
- Aspartate aminotransferase (AST)  $>2 \times$  and  $\leq 3 \times$  ULN; AST  $>3 \times$  and  $\leq 5 \times$  ULN; AST  $>5 \times$  and  $\leq 10 \times$  ULN; AST  $>10 \times$  ULN
- Bilirubin  $>2 \times$  and  $\leq 3 \times$  ULN; Bilirubin  $>3 \times$  ULN

In addition, a table will summarize the occurrence of events that satisfy the following versions of Hy’s Law:

- (ALT or AST  $>3 \times$  ULN and  $\leq 5 \times$ ULN) and total bilirubin  $>2 \times$  ULN;
- (ALT or AST  $>5 \times$  ULN and  $\leq 10 \times$ ULN) and total bilirubin  $>2 \times$  ULN;
- ALT or AST  $>10 \times$  ULN and total bilirubin  $>2 \times$  ULN

#### E.1.2 Serum and Urine Pregnancy Tests

Serum pregnancy test for females of childbearing potential will be performed at screening visit 2 and will be used for the subject’s inclusion or exclusion. A urine pregnancy test will be performed during the screening visit and the results must be negative before subject’s initiation of study drug. Additional pregnancy tests may be conducted during the study to establish the absence of pregnancy based on the investigator’s clinical judgment or as required by local regulations.

A by-subject listing of serum and urine pregnancy tests will be provided.

#### E.1.3 Urine Albumin-to-creatinine Ratio (uACR)

A random urine spot sample is collected at the investigative site during the Baseline, Weeks 28, 52, 104, 156, 208 and end of treatment (EOT) to assess the urine albumin-to-creatinine ratio (uACR). A by-subject listing of change and percentage change from baseline in uACR will be provided, as well as geometric means (logarithmic scale) over time. The number and percent of subjects with a percent change in uACR exceeding 30% (in either direction) will be presented.

### **E.1.4 Complete Blood Count**

The following components of the complete blood count (CBC) will be analyzed:

- mean corpuscular volume
- mean corpuscular Hb
- mean corpuscular Hb Concentration
- red cell distribution width
- white blood cell count with differential (neutrophils, lymphocytes, monocytes, eosinophils, and basophils)
- platelets
- hematocrit
- RBC counts

Summary statistics will be provided for the following:

- Each component of the CBC by treatment group.
- Change from baseline in each component of the CBC by treatment group.
- Changes from baseline category to the worst reported Common Terminology Criteria for Adverse Events (CTCAE) grade in each analysis time period in Year 1 and Weeks 52 to EOS.

A by-subject listing of all components of the CBC will be provided by treatment group.

In addition for white blood cells (WBC), lymphocytes, neutrophils, and platelets, a summary of the number and percentage of subjects experiencing abnormal values will be presented by treatment group and analysis time period. This summary will indicate the worst reported Common Terminology Criteria for Adverse Events (CTCAE) grade for the analysis time period for all subjects experiencing CTCAE grade 3 values or higher.

### **E.1.5 Chemistry and Estimated Glomerular Filtration Rate (eGFR)**

The following laboratory parameters (with preferred units in parentheses) will be analyzed:

- Sodium (mmol/L)
- Potassium (mmol/L)
- Bicarbonate (mEq/L)
- Chloride (mmol/L)
- Calcium (mmol/L)
- Magnesium (mEq/L)
- Phosphorus (mmol/L)
- Phosphate (mmol/L)
- Glucose (mg/dL)
- Creatinine (umol/L)
- Blood urea nitrogen (mg/dL)
- Creatine phosphokinase (U/L)
- Uric acid (umol/L)
- Albumin (g/dL)
- Total protein (g/L)
- Total bilirubin (umol/L)
- Alkaline phosphatase (U/L)
- Alanine aminotransferase (ALT) (U/L)
- Aspartate aminotransferase (AST) (U/L)
- Lactate dehydrogenase (U/L)

## Statistical Analysis Plan AKB-6548-CI-0014 and AKB-6548-CI-0015

- Total cholesterol (mg/dL)
- Low-density lipoprotein (LDL) cholesterol (mg/dL)
- High-density lipoprotein (HDL) cholesterol (mg/dL)
- Triglycerides (mg/dL)
- Derived parameter: non-HDL-cholesterol (= total cholesterol minus HDL cholesterol) (mg/dL)
- Estimated glomerular filtration rate (eGFR) (calculated from serum creatinine) (mL/min/1.73 m^2).

Summary statistics will be provided for the following:

- All chemistry parameters and eGFR by treatment group.
- Change (absolute and percent) from baseline in chemistry and eGFR by treatment group.
- Changes from baseline category to the worst reported Common Terminology Criteria for Adverse Events (CTCAE) grade in each analysis time period in Year 1 and Weeks 52 to EOS.

The eGFR will be calculated from serum creatinine by the formula of the 2009 Chronic Kidney Disease Epidemiological Collaboration (CKD-EPI). See [Appendix B](#) of the protocols.

A by-subject listing of chemistry and eGFR will be provided by treatment group. The categories for the shift tables will be based on CTCAE grades if available.

In addition, a summary of the number and percentage of subjects experiencing clinically significant values for each of the following parameter definitions will be presented by analysis time period:

- Decrease in eGFR  $\geq 40\%$  from baseline.
- Potassium  $>6.0$  mmol/L.

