7.5.2 Subject Completion

A subject will be considered as having completed the study, regardless of whether they are on or off study medication (vadadustat or darbepoetin alfa), if the subject is followed until global study completion (end of trial). The table outlines the different categories of subjects and handling the global study completion activities.

Subject Status at time of Global Study Completion	End of Treatment (EOT)	End of Study (EOS)
Subject on study medication (includes those on temporary interruption)	After announcement of global study completion: 
 • Perform EOT visit • Perform the Follow-up visit 4 weeks after EOT visit and include End of Study (EOS) subject status 	Not applicable The EOS subject status will be captured as part of the Follow-up visit
Subject permanently discontinued study medication and continues to be followed in the study	At time of permanent discontinuation of study medication: 
 • Perform EOT visit • Perform the Follow-up visit 4 weeks after EOT visit 	Optimal data collection would include the following assessments: 
 • EOS subject status (must collect at minimum) • MACE Endpoint Questionnaire • AE Assessment
Subject Lost to Follow-up	Not applicable	Work with third party vendor to ascertain vital status and complete EOS subject status If subject-site contact is reestablished and possible, collect available information for EOS subject status
Subject Withdrawn Consent	Not applicable	Complete the EOS subject status form at time of withdrawal of consent, absolute refusal of ALL methods of MACE and health status follow-up

Subject Death	Not applicable	Complete the EOS subject status form at the time of death (see Section 10 Adverse Events for more details on other actions related to reporting a death)
---------------	----------------	--

The need for rescue therapy does not constitute study completion and is not a criterion for subject withdrawal from the study. Also, the occurrence of a safety endpoint, or if a subject progressed to chronic dialysis dependent CKD (DD-CKD), does not constitute study completion and is not a criterion for subject withdrawal from the study or study medication (vadadustat or darbepoetin alfa).

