### 5.1 Visit and Analysis Time Period Classification

The time windows in this section reflect the administrative range around each visit for analysis. They are wider than those stated in the protocol to reduce missing values by capturing as many observation dates as possible. [Table 1](#) provides the convention to classify assessment dates into protocol-defined visits and analysis time periods for assessments at every visit, such as Hb and vital signs. [Table 1](#) will also be used for liver function assessments.

[Table 2](#) presents visit windows for values according to a slightly less frequent assessment schedule, i.e., the iron indices. And, [Table 2](#) will also be used for all other assessments, such as periodic complete blood count (CBC) with differential, chemistry laboratory tests, C-reactive protein (CRP), urine albumin-to-creatinine ratio (uACR) and lipids etc.

Unless otherwise specified, all assessments will be mapped to visit windows on the basis of the date of the assessment relative to the first dose date (i.e., Study Day), regardless of subject disposition or the CRF page completed, e.g., "Unscheduled", "End of Treatment", "End of Study", scheduled visit number. Similarly, all values collected within a reporting period will be considered for identification of safety events of interest.

If more than 1 laboratory-based efficacy outcome value (e.g., Hb, ferritin, hepcidin, TSAT, serum iron, TIBC, and lipids) is available in an analysis time period post-baseline, the average of all observed values (at most 1 per day) will be assigned to that period. For example, the window for the primary efficacy outcome, analysis time period 3, includes any Hb value (at most 1 per day) assessed between Study Days 155 to 266, corresponding to Weeks 24, 28, 32, and 36 (Visits 10 through 13).

Efficacy evaluations will use Hb values as assessed by the central laboratory. (Local HemoCue Hb values are used only for dose adjustments.)

When more than 1 assessment is made for other measures (not part of laboratory-based efficacy) within a given visit window post-baseline, the value of the assessment closest to the end of the window is the value associated with that visit for summaries over time. Most summaries of results by visit (e.g., laboratory or vital sign results for general safety) will use the single value

Statistical Analysis Plan AKB-6548-CI-0014 and AKB-6548-CI-0015

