**12 OTHER EXPLORATORY ANALYSES**

In addition to the planned analyses described above, the study team will likely perform many other descriptive analyses of efficacy and safety. For example, the team is likely to provide descriptions of the trajectory of subjects who transition to chronic dialysis, which will include the figures for Hb and other labs after the date of initiation of dialysis.

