**Table B 1. Outcome Variables and Covariates in the Multiple Imputation Models**

| Type       | Variable a | Description  | Baseline, Post, Outcome | Levels |
|------------|-----------------------|--|-------------------------|--------|
| Continuous | HBBL                  | Baseline Hb  | Baseline                | n/a    |
| Continuous | HBS1                  | Hb in Weeks 2-8  | Post                    | n/a    |
| Continuous | HBS2                  | Hb in Weeks 10-20  | Post                    | n/a    |
| Continuous | HBS3                  | Hb in PEP (Weeks 24-36)  | HBCHGS3, HBRNGS3        | n/a    |
| Continuous | HBS4                  | Hb in SEP (Weeks 40-52)  | HBCHGS4, HBRNGS4        | n/a    |
| Continuous | TIBCBL                | Baseline TIBC  | Baseline                | n/a    |
| Continuous | HEPCNBL               | Baseline hepcidin  | Baseline                | n/a    |
| Continuous | FERRBL                | Baseline ferritin  | Baseline                | n/a    |
| Continuous | UACRBL                | Baseline uACR (PRO2 only)  | Baseline                | n/a    |
| Continuous | CRPBL                 | Baseline CRP   | Baseline                | n/a    |
| Continuous | TSATBL                | Baseline TSAT  | Baseline                | n/a    |
| Continuous | EGFRBL                | Baseline eGFR (PRO2 only)  | Baseline                | n/a    |
| Continuous | TIBCS3                | TIBC in PEP (Weeks 24-36)  | Post                    | n/a    |
| Continuous | HEPCNS3               | Hepcidin in PEP (Weeks 24-36)  | Post                    | n/a    |
| Continuous | FERRS3                | Ferritin in PEP (Weeks 24-36)  | Post                    | n/a    |
| Continuous | UACRS3                | uACR in PEP (Weeks 24-36) (PRO2 only)  | Post                    | n/a    |
| Continuous | CRPS3                 | CRP in PEP (Weeks 24-36)   | Post                    | n/a    |
| Continuous | TSATS3                | TSAT in PEP (Weeks 24-36)  | Post                    | n/a    |
| Continuous | EGFRS3                | eGFR in PEP (Weeks 24-36) (PRO2 only)  | Post                    | n/a    |
| Continuous | ESABL                 | Baseline ESA dose  | Baseline                | n/a    |
| Continuous | TDIALBL               | Time on dialysis prior to Screening Visit 1 (INNO2 only)                               | Baseline                | n/a    |
| Continuous | AGE                   | Age  | Baseline                | n/a    |

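### Creatinine-based eGFR recorded after chronic dialysis starts enters the descriptive renal safety tables and can shrink, or in the extreme reverse, a between-arm renal deficit

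*SAP*

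**What the plan says.** - **Subjects continue after dialysis starts.** Protocol (Amendment 7-COL) 7.5.2 says that progression to chronic dialysis "does not constitute study completion and is not a criterion for subject withdrawal from the study or study medication". Sections 8.4.4.1 and 8.4.4.2 and Appendices C and D provide for dosing after that point.
- **Sampling continues.** Protocol 9.2.2 schedules chemistry, creatinine and eGFR throughout treatment. It has no exemption for dialysed subjects and no timing relative to a dialysis session.
- **Values enter by date.** Under SAP 5.1, "all assessments will be mapped to visit windows on the basis of the date of the assessment relative to the first dose date", whatever the subject's disposition. The same section uses all values in a reporting period to identify safety events.
- **Summaries.** SAP E.1.5 tabulates eGFR by arm and "Change (absolute and percent) from baseline in chemistry and eGFR by treatment group". It adds "a summary of the number and percentage of subjects experiencing clinically significant values", one of which is an eGFR decrease of at least 40%, by analysis time period.
- **Source of eGFR.** "The eGFR will be calculated from serum creatinine by the formula of the 2009 Chronic Kidney Disease Epidemiological Collaboration (CKD-EPI"). Protocol Appendix B prints the equation; it has no term for dialysis.
- **Dialysis is recognised elsewhere.** SAP 6.3.6 makes chronic dialysis a CKD-progression event. Protocol 11.7.1 has a MACE analysis censored when chronic dialysis starts. SAP Section 12 foresees "descriptions of the trajectory of subjects who transition to chronic dialysis", including laboratory figures after that date. No corresponding rule appears in SAP E.1.5, 5.1 or 5.4.

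**The concern.** Starting chronic dialysis is among the worst renal outcomes in this population, yet it can lower measured creatinine and so raise calculated eGFR with no renal recovery. If the arms differ in dialysis starts, the by-arm eGFR table then mixes native kidney function with creatinine clearance by a machine. A real renal harm could look smaller than it is, and subjects already counted with a decrease of at least 40% could drop out of the count in later periods. Dialysis starts are foreseeable: eligibility has no lower eGFR limit, requires only that dialysis is not expected within 6 months of Screening, and a baseline eGFR below 15 is a planned subgroup.

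**Working it through.** The plan gives no figure to reproduce here. The check applies the equation in Protocol Appendix B to assumed creatinine values, because the documents give neither on-dialysis creatinine nor the share of subjects dialysed.

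**1. Equation.** For a man aged 65, race coefficient not applied, and creatinine above 0.9 mg/dL: eGFR = 141 × (SCr/0.9)^-1.209 × 0.993^65.

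| SCr (mg/dL) | 3 | 3.5 | 4 | 5 | 6 | 7 | 8 |
|---|---|---|---|---|---|---|---|
| eGFR | 20.8 | 17.3 | 14.7 | 11.2 | 9.0 | 7.5 | 6.4 |

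**2. Flag threshold.** A 40% fall needs SCr of at least 0.6^(-1/1.209) = 1.53 × baseline. A subject with baseline eGFR 20 and creatinine 6 is at 9.0/20 - 1 = -55% (flagged). At creatinine 4 on dialysis the same subject shows 14.7/20 - 1 = -27% (not flagged).

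**3. Equal kidney disease, unequal dialysis.** Assume that 30% of each arm has native creatinine 7 (eGFR 7.5), the rest have creatinine 3.3 (eGFR 18.6), and baseline creatinine is 3.0. Dialysed shares are 20% and 10%, and on-dialysis creatinine is c. The true difference is 0. Displayed difference = (0.20 - 0.10) × [eGFR(c) - 7.5].

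**4. Extra dialysis reflects extra failure.** Now only the dialysed subjects have failed. True difference = 0.10 × (7.5 - 18.6) = -1.1. Displayed difference = 0.10 × [eGFR(c) - 18.6].

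| c (mg/dL) | Step 3 displayed (true 0) | Step 3 count of ≥40% falls | Step 4 displayed (true -1.1) |
|---|---|---|---|
| 3 | +1.3 | 10% v 20% | +0.2 |
| 3.5 | +1.0 | 10% v 20% | -0.1 |
| 4 | +0.7 | 10% v 20% | -0.4 |
| 5 | +0.4 | 30% v 30% | -0.7 |
| 6 | +0.15 | 30% v 30% | -1.0 |
| 7 | 0 | 30% v 30% | -1.1 |
| 8 | -0.1 | 30% v 30% | -1.2 |

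Differences are the arm with more dialysis minus the other, in mL/min/1.73 m². The counts refer to a period after dialysis has started; the flag threshold is 1.53 × 3.0 = 4.6 mg/dL. In step 4 the sign changes only when c is below 3.3, the level assumed for everyone else.

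**5. Exclusion alone.** Suppose that 90% of an arm has mean eGFR 20 and 10% are dialysed, with native eGFR 9.0 displayed as 14.7. The native mean is 0.9 × 20 + 0.1 × 9.0 = 18.9. The plan as written gives 0.9 × 20 + 0.1 × 14.7 = 19.5. Dropping the dialysed subjects gives 20.0. Exclusion therefore raises the mean further unless the table says whom it describes.

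**The case against.** - **Dialysis is already captured.** It is an event in the time-to-event CKD-progression endpoint and is always reported as a serious adverse event. The E.1.5 tables are descriptive under SAP Section 10. This stands and limits the importance. It does not make the eGFR table correct.
- **Few flags are lost.** All values in a period count toward safety events, so a subject who met the threshold before dialysis stays flagged in that period. The flag goes only in later periods, and only if every value there is below 1.53 × baseline. This stands.
- **Not everyone contributes.** SAP 2.2 plans no laboratory tests after permanent discontinuation, so only subjects who stay on drug after starting dialysis supply these values. This also stands.
- **Blinded review could settle it.** SAP Section 1 lets a blinded team add conventions, and 13.1 lets it exclude data before unblinding. That is a route to a rule, but no rule is yet written, and this issue can be foreseen.
- **Imputation.** A reader might infer that the primary analysis is distorted, because Table B 1 lists "eGFR in PEP (Weeks 24-36) (PRO2 only") among the imputation variables. The documents do not support that. The variable is absent from the Exhibit B 1 code, and it would at most help to predict missing hemoglobin.

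**Conclusion.** The defect is real but confined to the descriptive eGFR and creatinine summaries and the count of decreases of at least 40% in E.1.5. That post-dialysis values are included follows from continued sampling, mapping of all values by date and the absence of any exclusion; the SAP does not say so in words.

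A reader might infer that the arm with more dialysis starts will show the better eGFR. The documents do not support that as a general statement. Where extra dialysis reflects extra kidney failure, the usual effect is to shrink the deficit (-1.1 displayed as -0.7 to -0.1 for creatinine 5 to 3.5); reversal needs strong clearance, near creatinine 3. With equal native disease, the arm with more dialysis looks better by about 0.15 to 1.0 for creatinine 6 to 3.5, and there is no gain at 7 or above. All these sizes rest on assumed creatinine levels and dialysed shares.

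Nor do the documents support reading this as a flaw in the CKD-progression endpoint, MACE or the primary hemoglobin endpoint. It is worth correcting before database lock because it affects a by-arm renal table in a kidney-disease trial.

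**What to change.** In SAP E.1.5:

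1. Exclude eGFR and serum creatinine from the by-visit means and from the absolute and percent changes, from the date chronic dialysis starts.
2. Show the number of subjects on chronic dialysis beside each visit or period, by arm, and label the means as conditional on being dialysis-free. Step 5 of the working shows why exclusion without this is not enough.
3. Replace the count with a decrease in eGFR of at least 40% or on chronic dialysis, with the two components shown separately. Dialysed subjects then stay counted in later periods without being mislabelled: a subject with baseline 12 who starts dialysis at 9 has fallen by only 25%.

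The uACR summaries and the Table B 1 variables need no change on this ground.

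The cost is one derivation rule. It should need no new data: dialysis start is reportable as a serious adverse event, is an event in SAP 6.3.6, and anchors the figures in Section 12. The downside is fewer subjects in the late-visit means, which then apply only to dialysis-free subjects. Sample size, power and patient management do not change.

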### **E.1.6 C-reactive protein and Vascular Endothelial Growth Factor**

Summary statistics will be provided for the following:

- C-reactive protein (CRP) and vascular endothelial growth factor (VEGF) by treatment group.
- Change (absolute and percent) from baseline in CRP and VEGF by treatment group.

A by-subject listing of CRP and VEGF will be provided by treatment group.

### **E.1.7 Erythropoietin**

Blood samples for erythropoietin (Epo) analysis are obtained at Baseline and at Weeks 4, 12, 28, and 52.

A by-subject listing and a summary table of Epo (absolute level and change from baseline) by treatment group and time of collection will be provided.

## **E.2. Vital Signs, ECGs, and Physical Findings**

### **E.2.1 Vital Signs and Weight**

Body weight and the following vital signs will be summarized:

- Systolic BP
- Diastolic BP
- Heart rate
- Respiratory rate
- Body temperature.

Summary statistics will be provided for the following:

- Vital Signs and Weight by treatment group.
- Change from baseline in Vital Signs and Weight by treatment group.
- The number and percentage of subjects experiencing the following findings by treatment group and by analysis time periods:
  - Systolic blood pressure (SBP)  $\geq 160$  mmHg or diastolic blood pressure (DBP)  $\geq 110$  mmHg
  - SBP  $\leq 90$  mmHg or DBP  $\leq 50$  mmHg
  - change in SBP or DBP in either direction  $\geq 20$  mmHg
  - Systolic blood pressure (SBP)  $\geq 180$  mmHg

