#### 10.4 Other Safety Endpoints

Vital signs and clinical laboratory values will be presented as outlined in [Appendix E](#).

The following additional safety endpoints will be presented:

- The number of usage of hypertensive medications added after first dose by study period/visit.

The separate MACE SAP will describe the methodology for the adjudicated analyses.

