**APPENDIX F. ADVERSE EVENTS OF SPECIAL INTEREST****F.1. Potential Risks**

The following potential risk factors will be presented as adverse events of special interest (AESI):

- Hypersensitivity: Hypersensitivity Standardised MedDRA Query (SMQ) Narrow
- Hyperkalemia: Hyperkaliemia MedDRA PT, Blood potassium abnormal MedDRA PT, Blood potassium increased MedDRA PT
- Hypertension: Hypertension MedDRA SMQ Narrow

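### The 20 mmHg blood pressure change row and the 30% uACR change count combine rises with falls, so neither shows direction; report increases and decreases separately

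*SAP*

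**What the plan says.** SAP E.2.1 (Vital Signs and Weight) lists four blood pressure findings, to be reported as number and percentage of subjects by treatment group and analysis time period. Three concern levels: a high row (SBP at least 160 or DBP at least 110 mmHg), a low row (SBP at most 90 or DBP at most 50 mmHg) and a row for SBP of at least 180 mmHg. The fourth concerns change: a "change in SBP or DBP in either direction" of at least 20 mmHg.

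SAP E.1.3 has one responder count for albuminuria: "The number and percent of subjects with a percent change in uACR exceeding 30% (in either direction) will be presented".

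Both sections also plan outputs that keep the sign. E.2.1 includes "Change from baseline in Vital Signs and Weight by treatment group". E.1.3 plans a by-subject listing of change and percentage change, "as well as geometric means (logarithmic scale) over time". The opening of Appendix E says that summary tables by visit "will be provided for all outcomes, observed and change from baseline, in this section".

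Elsewhere, Appendix F.1 lists "Hypertension: Hypertension MedDRA SMQ Narrow" among the adverse events of special interest, and Section 10.4 adds "The number of usage of hypertensive medications added after first dose by study period/visit".

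**The concern.** A large rise and a large fall in blood pressure are different safety findings, and the SAP names hypertension as a potential risk. A rise in uACR points to worsening and a fall to improvement. One unsigned percentage adds the two together. If an arm shifts, more subjects pass the upper cut-off and fewer pass the lower one, so the total moves less than either part.

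The SAP keeps direction in comparable places. The eGFR count in E.1.5 is a decrease of 40% or more. Table 4 separates high from low Hb and counts Hb increases. The level rows in E.2.1 separate high from low. Only these two change counts are unsigned, and no reason is given.

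At stake is how a descriptive table is read. Similar combined percentages in the two arms could be taken as reassurance when one arm has more rises and fewer falls.

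**Working it through.** The plan states no expected rate, SD or power for these counts, so there is no figure of its own to reproduce. What follows is an illustration.

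**Inputs from the SAP.** Cut-offs of 20 mmHg (E.2.1) and 30% (E.1.3); about 925 subjects per arm (Section 2.6).

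**Assumptions, not in the documents.** Change is measured from baseline and is normal, with mean 0 in the control arm and mean *m* in the other. The SD of SBP change is 12 to 25 mmHg. For uACR, the SD of the log ratio to baseline is 0.5 to 0.9.

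**Formulas for SBP.**
- P(rise) = 1 − Φ((20 − m)/SD)
- P(fall) = Φ((−20 − m)/SD)
- Combined = P(rise) + P(fall)
- Share cancelled = loss of falls ÷ gain of rises

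Worked case, SD 20 and m = 5: P(rise) goes from 1 − Φ(1.00) = 15.9% to 1 − Φ(0.75) = 22.7%. P(fall) goes from 15.9% to Φ(−1.25) = 10.6%. The sum goes from 31.7% to 33.2%.

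Results for m = +5 mmHg:

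| Assumed SD (mmHg) | Rises | Falls | Combined row | Share cancelled |
|---|---|---|---|---|
| 12 | 4.8% to 10.6% | 4.8% to 1.9% | 9.6% to 12.4% | 50% |
| 15 | 9.1% to 15.9% | 9.1% to 4.8% | 18.2% to 20.6% | 64% |
| 18 | 13.3% to 20.2% | 13.3% to 8.2% | 26.7% to 28.5% | 74% |
| 20 | 15.9% to 22.7% | 15.9% to 10.6% | 31.7% to 33.2% | 78% |
| 25 | 21.2% to 27.4% | 21.2% to 15.9% | 42.4% to 43.3% | 85% |

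As a yardstick only, since the tables are descriptive: at SD 18, 925 per arm and two-sided 0.05, power is about 98% for the rise row and 14% for the combined row.

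The planned row is met by SBP or DBP. A simulation with SBP SD 18, DBP SD 10, correlation 0.6 and a DBP shift half the SBP shift gives the same pattern at +5 mmHg: rises from about 14% to 21%, combined from about 28% to 30%.

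**uACR.** On the log scale the cut-offs are ln 1.3 and ln 0.7. For a true 20% rise in the geometric mean:

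| Assumed log SD | Rises | Falls | Combined count | Share cancelled |
|---|---|---|---|---|
| 0.5 | 30.0% to 43.6% | 23.8% to 14.1% | 53.8% to 57.7% | 71% |
| 0.7 | 35.4% to 45.4% | 30.5% to 22.1% | 65.9% to 67.5% | 84% |
| 0.9 | 38.5% to 46.5% | 34.6% to 27.5% | 73.1% to 73.9% | 90% |

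**Where cancellation is stronger or weaker.**
- Opposite shifts are the extreme. With arms at −5 and +5 mmHg (SD 18), the combined rate is 28.5% in both, while rises are 8.2% and 20.2%.
- A larger shift cancels less. At +10 mmHg the share is 27% to 73% over SD 12 to 25.
- Harm confined to a subset cancels little. If 10% of subjects shift by +30 mmHg (SD 18), rises gain 5.8 points, falls lose 1.3 and the combined row gains 4.5.

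**The case against.** The strongest reply is that a reader would not depend on these two counts. A reader might infer from the cancellation that the blood pressure and uACR tables cannot show harm. The documents do not support that. Three of the four blood pressure findings in E.2.1 are directional, and signed mean change is planned in the same section. Under the assumptions above, the mean change would detect +5 mmHg with about 99% to 100% yardstick power over SD 12 to 25. If SBP is assumed to have mean 138 and SD 19, the share at or above 160 moves from 12.3% to 18.5%. The uACR geometric mean would detect a 20% rise with 99% to 100%. Reported hypertension and added blood pressure medication are further directional outputs.

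The reply also notes that every SD is assumed, that cancellation is conditional on the size and shape of the shift, that Section 10 makes most safety analysis descriptive with no decision rule on these rows, and that the table shells are not available to check.

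All of that stands, and it limits the point to two counts. It does not remove it. A mean does not say how many subjects had a large rise. The level rows miss a subject whose SBP goes from 125 to 150 mmHg, and they count one who was already at 160 at baseline. uACR has no other responder count; its by-subject listing holds the information but does not tabulate it.

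**Conclusion.** The point holds for the two counts named. That rises and falls are combined is plain from the text and needs no assumption. The counts cannot show direction, and they are insensitive to a modest uniform shift: about 50% to 85% of a +5 mmHg signal cancels over assumed SDs of 12 to 25 mmHg. Cancellation is weaker for larger shifts and slight when only a subset is affected, so the loss should not be stated as general.

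The point does not extend to the safety package as a whole, which has several outputs able to reveal a shift. What is missing is the proportion of subjects with a large individual rise or fall, by arm. It affects neither sample size nor any formal inference. Severity: a cheap, optional improvement.

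**What to change.** In E.2.1, report four rows by arm and analysis period: SBP rise of at least 20 mmHg, SBP fall of at least 20 mmHg, DBP rise of at least 20 mmHg and DBP fall of at least 20 mmHg. In E.1.3, report uACR increase above 30% and uACR decrease above 30% separately by arm. The combined rows can be kept alongside; deleting a prespecified output is unnecessary.

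The data and cut-offs are unchanged. The cost is SAP wording, the table shells and a few more table rows.
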